13.2 Animal Toxicology

In single-dose rodent studies using subcutaneous injection of teriparatide, no mortality was seen in rats given doses of 1000 mcg/kg (540 times the human dose based on surface area, mcg/m²) or in mice given 10,000 mcg/kg (2700 times the human dose based on surface area, mcg/m²).

In a long-term study, skeletally mature ovariectomized female monkeys (N=30 per treatment group) were given either daily subcutaneous teriparatide injections of 5 mcg/kg or vehicle. Following the 18-month treatment period, the monkeys were removed from teriparatide treatment and were observed for an additional 3 years. The 5 mcg/kg dose resulted in systemic exposures that were approximately 6 times higher than the systemic exposure observed in humans following a subcutaneous dose of 20 mcg (based on AUC comparison). Bone tumors were not detected by radiographic or histologic evaluation in any monkey in the study.

14 CLINICAL STUDIES

14.1 Treatment of Osteoporosis in Postmenopausal Women

The safety and efficacy of once-daily FORTEO, median exposure of 19 months, were examined in a double-blind, multicenter, placebo-controlled clinical study of 1637 postmenopausal women with osteoporosis (FORTEO 20 mcg, n=541).

All women received 1000 mg of calcium and at least 400 IU of vitamin D per day. Baseline and endpoint spinal radiographs were evaluated using the semiquantitative scoring. Ninety percent of the women in the study had 1 or more radiographically diagnosed vertebral fractures at baseline. The primary efficacy endpoint was the occurrence of new radiographically diagnosed vertebral fractures defined as changes in the height of previously undeformed vertebrae. Such fractures are not necessarily symptomatic.

Effect on Fracture Incidence

New Vertebral Fractures — FORTEO, when taken with calcium and vitamin D and compared with calcium and vitamin D alone, reduced the risk of 1 or more new vertebral fractures from 14.3% of women in the placebo group to 5.0% in the FORTEO group. This difference was statistically significant (p<0.001); the absolute reduction in risk was 9.3% and the relative reduction was 65%. FORTEO was effective in reducing the risk for vertebral fractures regardless of age, baseline rate of bone turnover, or baseline BMD (see Table 2).

Table 2. Effect of FORTEO on Risk of Vertebral Fractures in Postmenopausal Women with Osteoporosis

[figure not shown]
	Percent of Women With Fracture			
	FORTEO (N=444)	Placebo (N=448)	Absolute Risk Reduction (%, 95% CI)	Relative Risk Reduction (%, 95% CI)
New fracture (≥1)	5.0 ^a	14.3	9.3 (5.5-13.1)	65 (45-78)
1 fracture	3.8	9.4		
2 fractures	0.9	2.9		
≥3 fractures	0.2	2.0		

^a p≤0.001 compared with placebo.

New Nonvertebral Osteoporotic Fractures — FORTEO significantly reduced the risk of any nonvertebral fracture from 5.5% in the placebo group to 2.6% in the FORTEO group ($p < 0.05$). The absolute reduction in risk was 2.9% and the relative reduction was 53%. The incidence of new nonvertebral fractures in the FORTEO group compared with the placebo group was ankle/foot (0.2%, 0.7%), hip (0.2%, 0.7%), humerus (0.4%, 0.4%), pelvis (0%, 0.6%), ribs (0.6%, 0.9%), wrist (0.4%, 1.3%), and other sites (1.1%, 1.5%), respectively.

The cumulative percentage of postmenopausal women with osteoporosis who sustained new nonvertebral fractures was lower in women treated with FORTEO than in women treated with placebo (*see* Figure 1).

Figure 1. Cumulative Percentage of Postmenopausal Women with Osteoporosis Sustaining New Nonvertebral Osteoporotic Fractures

Effect on Bone Mineral Density (BMD)

FORTEO increased lumbar spine BMD in postmenopausal women with osteoporosis. Statistically significant increases were seen at 3 months and continued throughout the treatment period. Postmenopausal women with osteoporosis who were treated with FORTEO had statistically significant increases in BMD from baseline to endpoint at the lumbar spine, femoral neck, total hip, and total body (*see* Table 3).

Table 3. Mean Percent Change in BMD from Baseline to Endpoint^a in Postmenopausal Women with Osteoporosis, Treated with FORTEO or Placebo for a Median of 19 Months

	FORTEO N=541	Placebo N=544
Lumbar spine BMD	9.7 ^b	1.1
Femoral neck BMD	2.8 ^c	-0.7
Total hip BMD	2.6 ^c	-1.0
Trochanter BMD	3.5 ^c	-0.2
Intertrochanter BMD	2.6 ^c	-1.3

Ward's triangle BMD	4.2 ^c	-0.8
Total body BMD	0.6 ^c	-0.5
Distal 1/3 radius BMD	-2.1	-1.3
Ultradistal radius BMD	-0.1	-1.6

^a Intent-to-treat analysis, last observation carried forward.

^b p<0.001 compared with placebo.

^c p<0.05 compared with placebo.

FORTEO treatment increased lumbar spine BMD from baseline in 96% of postmenopausal women treated.

Seventy-two percent of patients treated with FORTEO achieved at least a 5% increase in spine BMD, and 44% gained 10% or more.

Both treatment groups lost height during the trial. The mean decreases were 3.61 and 2.81 mm in the placebo and FORTEO groups, respectively.

Bone Histology

The effects of teriparatide on bone histology were evaluated in iliac crest biopsies of 35 postmenopausal women treated for 12 to 24 months with calcium and vitamin D and teriparatide 20 or 40 mcg/day. Normal mineralization was observed with no evidence of cellular toxicity. The new bone formed with teriparatide was of normal quality (as evidenced by the absence of woven bone and marrow fibrosis).

14.2 Treatment to Increase Bone Mass in Men with Primary or Hypogonadal Osteoporosis

The safety and efficacy of once-daily FORTEO, median exposure of 10 months, were examined in a double-blind, multicenter, placebo-controlled clinical study of 437 men with either primary (idiopathic) or hypogonadal osteoporosis (FORTEO 20 mcg, n=151). All men received 1000 mg of calcium and at least 400 IU of vitamin D per day. The primary efficacy endpoint was change in lumbar spine BMD.

FORTEO increased lumbar spine BMD in men with primary or hypogonadal osteoporosis. Statistically significant increases were seen at 3 months and continued throughout the treatment period. FORTEO was effective in increasing lumbar spine BMD regardless of age, baseline rate of bone turnover, and baseline BMD. The effects of FORTEO at additional skeletal sites are shown in Table 4.

FORTEO treatment for a median of 10 months increased lumbar spine BMD from baseline in 94% of men treated.

Fifty-three percent of patients treated with FORTEO achieved at least a 5% increase in spine BMD, and 14% gained 10% or more.

Table 4. Mean Percent Change in BMD from Baseline to Endpoint^a in Men with Primary or Hypogonadal Osteoporosis, Treated with FORTEO or Placebo for a Median of 10 Months

	FORTEO N=151	Placebo N=147
Lumbar spine BMD	5.9 ^b	0.5
Femoral neck BMD	1.5 ^c	0.3
Total hip BMD	1.2	0.5
Trochanter BMD	1.3	1.1
Intertrochanter BMD	1.2	0.6
Ward's triangle BMD	2.8	1.1
Total body BMD	0.4	-0.4
Distal 1/3 radius BMD	-0.5	-0.2
Ultradistal radius BMD	-0.5	-0.3

^a Intent-to-treat analysis, last observation carried forward.

^b p<0.001 compared with placebo.

^c p<0.05 compared with placebo.

14.3 Treatment of Men and Women with Glucocorticoid-Induced Osteoporosis

The efficacy of FORTEO for treating glucocorticoid-induced osteoporosis was assessed in a randomized, double-blind, active-controlled trial of 428 patients (19% men, 81% women) aged 22 to 89 years (mean 57 years) treated with ≥ 5 mg/day prednisone or equivalent for a minimum of 3 months. The duration of the trial was 18 months with 214 patients exposed to FORTEO. In the FORTEO group, the baseline median glucocorticoid dose was 7.5 mg/day and the median duration of glucocorticoid use was 1.5 years. The mean (SD) baseline lumbar spine BMD was 0.85 ± 0.13 g/cm² and lumbar spine BMD T-score was -2.5 ± 1 (number of

standard deviations below the mean BMD value for healthy adults). A total of 30% of patients had prevalent vertebral fracture(s) and 43% had prior non-vertebral fracture(s). The patients had chronic rheumatologic, respiratory or other diseases that required sustained glucocorticoid therapy. All patients received 1000 mg of calcium plus 800 IU of vitamin D supplementation per day.

Because of differences in mechanism of action (anabolic vs. anti-resorptive) and lack of clarity regarding differences in BMD as an adequate predictor of fracture efficacy, data on the active comparator are not presented.

Effect on Bone Mineral Density (BMD)

In patients with glucocorticoid-induced osteoporosis, FORTEO increased lumbar spine BMD compared with baseline at 3 months through 18 months of treatment. In patients treated with FORTEO, the mean percent change in BMD from baseline to endpoint was 7.2% at the lumbar spine, 3.6% at the total hip, and 3.7% at the femoral neck ($p < 0.001$ all sites). The relative treatment effects of FORTEO were consistent in subgroups defined by gender, age, geographic region, body mass index, underlying disease, prevalent vertebral fracture, baseline glucocorticoid dose, prior bisphosphonate use, and glucocorticoid discontinuation during trial.

16 HOW SUPPLIED/STORAGE AND HANDLING

16.1 How Supplied

The FORTEO delivery device (pen) is available in the following package size:

- 2.4 mL prefilled delivery device NDC 0002-8400-01 (MS8400).

16.2 Storage and Handling

- The FORTEO delivery device should be stored under refrigeration at 2° to 8°C (36° to 46°F) at all times.
- Recap the delivery device when not in use to protect the cartridge from physical damage and light.
- During the use period, time out of the refrigerator should be minimized; the dose may be delivered immediately following removal from the refrigerator.
- Do not freeze. Do not use FORTEO if it has been frozen.

17 PATIENT COUNSELING INFORMATION

See Medication Guide.

17.1 Potential Risk of Osteosarcoma and Voluntary FORTEO Patient Registry

Patients should be made aware that in rats, teriparatide caused an increase in the incidence of osteosarcoma (a malignant bone tumor) that was dependent on dose and treatment duration. Patients should be encouraged to enroll in the voluntary FORTEO Patient Registry, which is designed to collect information about any potential risk of osteosarcoma in patients who have taken FORTEO. Enrollment information can be obtained by calling [name], or by visiting www.forteoregistry.rti.org.

17.2 Orthostatic Hypotension

FORTEO should be administered initially under circumstances where the patient can immediately sit or lie down if symptoms occur. Patients should be instructed that if they feel lightheaded or have palpitations after the injection, they should sit or lie down until the symptoms resolve. If symptoms persist or worsen, patients should be instructed to consult a physician before continuing treatment [*see Warnings and Precautions (5.7)*].

17.3 Hypercalcemia

Although symptomatic hypercalcemia was not observed in clinical trials, physicians should instruct patients taking FORTEO to contact a health care provider if they develop persistent symptoms of hypercalcemia (e.g., nausea, vomiting, constipation, lethargy, muscle weakness).

17.4 Other Osteoporosis Treatment Modalities

Patients should be informed regarding the roles of supplemental calcium and/or vitamin D, weight-bearing exercise, and modification of certain behavioral factors such as cigarette smoking and/or alcohol consumption.

17.5 Use of Delivery Device (Pen)

Patients and caregivers who administer FORTEO should be instructed on how to properly use the delivery device (refer to *User Manual*), properly dispose of needles, and be advised not to share their delivery device with other patients. The contents of the delivery device should NOT be transferred to a syringe.

Each FORTEO delivery device can be used for up to 28 days including the first injection from the delivery device. After the 28-day use period, discard the FORTEO delivery device, even if it still contains some unused solution.

17.6 Availability of Medication Guide and User Manual

Patients should read the *Medication Guide* and delivery device (pen) *User Manual* before starting therapy with FORTEO and re-read them each time the prescription is renewed. Patients need to understand and follow the instructions in the FORTEO delivery device *User Manual*. Failure to do so may result in inaccurate dosing.

Literature revised: March 21, 2012

Marketed by: Lilly USA, LLC
Indianapolis, IN 46285, USA
www.forteo.com

Copyright © 2002, 2012, Eli Lilly and Company. All rights reserved.

PA097FSAM01

24.14 Blood Draw Amounts

07-D-0016 Blood Draw Amounts

	Screening	V0	V1	V2	V3	V4	V5	V6	V7	V8	V9	V10	V11	Cumulative
	2-6 weeks	Month	mls											
Blood Tests														
DNA Testing - if indicated (not included in protocol)														
Chem 20 (4ml)	4	4	4	4	4	4	4	4	4	4	4	4	4	52
Complete blood count (3ml)	3	3	3	3	3	3	3	3	3	3	3	3	3	39
Mineral panel or calcium level (4ml) - as needed	8	32	4	4	4	4	4	4	4	4	4	4	4	
Thyroid Panel (4ml)	4	4	4	4	4	4	4	4	4	4	4	4	4	84
25-OH-VitD (5ml)	5	5	5	5	5	5	5	5	5	5	5	5	5	52
1,25 (OH) ₂ (4ml)	4	4	4	4	4	4	4	4	4	4	4	4	4	65
Intact PTH (3ml)	3	3	3	3	3	3	3	3	3	3	3	3	3	52
BSAP (4ml)		4	4	4	4	4	4	4	4	4	4	4	4	39
Osteocalcin (3ml)		3	3	3	3	3	3	3	3	3	3	3	3	48
Ionized calcium (1ml)	1	1	1	1	1	1	1	1	1	1	1	1	1	36
Research Blood for sample storage (4 ml)		4	4	4	4	4	4	4	4	4	4	4	4	13
24-hr blood sampling (4 mls X 13= 52ml)				52										48
Acute care and mineral panels for day 1 at 8 am, 12 pm, 4 pm, 8 pm, 8am on day 2		20												52
FGF-23 (4ml)		4												20
Total (ml)	32	91	39	91	39	604

1. PURPOSE OF THIS DOCUMENT

Several journal publications are expected from the study. This is an abbreviated statistical analysis plan with this document's primary focus on the statistical methods that will be used for the main publication. The safety analyses for this study have already been reported to the DSMB and will not be discussed further except to note that the tables and listings generated for the DSMB will be provided.

2. PROTOCOL SUMMARY

2.1 Study Objectives

The primary objective of this study is to evaluate the skeletal effects of hormone replacement therapy with synthetic human parathyroid 1-34 hormone (hPTH) in hypoparathyroidism

2.2 Overall Study Design and Plan

Copied from the protocol:

This study will treat hypoparathyroid individuals with synthetic human PTH 1-34 (hPTH) for up to 5 years, periodically assessing skeletal changes through biochemical markers and iliac-crest bone biopsies, which will allow for ultrastructural, cellular, and molecular analyses.

As revised in April 2010, the “current” protocol involves the recruitment of 36 new subjects (not previously enrolled) with hypoparathyroidism and the re-enrollment of qualifying subjects from the original protocol who were either on conventional therapy (calcium and calcitriol) or on hPTH therapy. All newly enrolled subjects will be placed on conventional therapy for 2 to 6 months (\pm 1 month), have a baseline bone biopsy performed at the start of hPTH therapy, and have their second biopsy performed after 1, 2, or 4 years of hPTH therapy, with the timing of the second biopsy determined by random assignment. The subjects on conventional therapy under the previous version of the protocol were randomized to a second biopsy at year 1, 2, or 4; however, their pre-conventional therapy biopsy will be used as their baseline biopsy. Subjects who were receiving hPTH under the previous version of the protocol are being maintained on hPTH in a separate group as a means to continue their care and to describe the effects of hPTH therapy on bone and markers of bone metabolism over time. Those subjects will not have another biopsy performed. All new and re-enrolled subjects will receive hPTH therapy for a maximum of 5 years.

Subjects will be initiated on hPTH at a starting dose of 0.2 μ g/kg/dose subcutaneously twice a day (study month 0). Subjects currently on hPTH therapy 3 times per day under the previous version of the protocol will be placed on hPTH 2 times per day, initially keeping the total daily dose the same. Over the 5-year course of hPTH therapy, the subjects will have their blood and urine measured repeatedly and evaluated by the study investigators, who will adjust subjects’ hPTH dosing according to a standardized algorithm. During hPTH therapy, subjects will visit the NIH Clinical Center every 6 months for outcome assessments. At the conclusion of the 5-year treatment period, subjects will be transitioned back to conventional care and followed for a

minimum of 3 months before returning them to care under their own physicians. All subjects, including those who discontinue hPTH prior to 5 years, will be asked to return for a final, follow-up visit approximately 6 months after the start of the post-hPTH stabilization phase (i.e., the initiation of transition to conventional care).

With a study period of approximately 6 years, the duration of the active phase of the study will be 9 years. New subjects will have 13 NIH visits, subjects currently on conventional care will have 12 NIH visits, and subjects currently on hPTH therapy will have up to 9 visits, depending on the amount of time they have been treated with hPTH under the previous version of the protocol. Additional visits may occur in order to evaluate adverse events.

The study design diagram and the schedule of events may be found in Appendices to the protocol.

2.3 Study Population

Copied from the protocol:

This study will enroll up to 69 subjects with physician-diagnosed hypoparathyroidism. Under the current protocol, 36 new subjects (i.e., not previously enrolled) with physician-diagnosed hypoparathyroidism who meet the revised eligibility criteria listed below will be enrolled. Previously enrolled subjects who were on conventional therapy for hypoparathyroidism were re-evaluated under the revised eligibility criteria and re-consented and re-enrolled if they were eligible and interested.

Previously enrolled subjects who were on hPTH therapy were re-consented and allowed to continue on hPTH therapy in the current protocol as a separate group that would not enter the randomization nor have any additional biopsies performed. However, they will return to the NIH for 6-month follow-up visits and assessments. Those subjects on hPTH at the time of re-consent were not re-assessed using the revised criteria, and their study data will be analyzed separately from the other subjects' data.

3. GENERAL ANALYSIS AND REPORTING CONVENTIONS

- Categorical variables will be summarized using counts (n) and percents (%) and will be presented in the form n (%).
- Standard deviations and confidence limits will be reported at 1 more significant digit than the mean.
- Order statistics including median, min and max will be reported to the same level of precision as the original observations. If any values are calculated to have more significant digits then the value should be rounded so that it is the same level of precision as the original data.
- Following SAS default rules, the median will be reported as the average of the two middle numbers if the dataset contains even numbers.
- No preliminary rounding should be performed; rounding should only occur after analysis. To round, consider digit to right of last significant digit: if < 5 then round down, if ≥ 5 then round up.
- All analysis will be performed using the SAS System version 9.4.

4. ANALYSIS POPULATIONS

There are 3 Study Cohorts for purposes of analysis:

Cohort 1: subjects who received hPTH under the original protocol;

Cohort 2: subjects who received conventional care in the original protocol and who re-enrolled into the current protocol and who were treated with hPTH;

Cohort 3: new subjects who initially enrolled into the current protocol.

Subjects in cohort 1 will be analyzed separately from the other subjects; only safety analyses will be conducted on this cohort. Subjects in cohorts 2 and 3 will be combined, and efficacy and safety analyses will be conducted on this group. However, the timing of the baseline biopsy relative to the on-treatment biopsy differs in cohorts 2 and 3. For cohort 2 there was a much longer period of time between the baseline biopsy and their 1, 2, or 4 year on hPTH biopsy, in that the baseline period also include their entire period being on conventional care. Whereas for cohort 3, baseline biopsies were taken immediately prior to beginning hPTH. Because of this difference, all efficacy analyses will be repeated on subjects in cohort 3 alone.

Safety Population: The Safety Population will consist of all enrolled subjects (all cohorts) who have started any study treatment including, but not limited to, conventional care. This population will be used for safety data summaries.

Bone Biopsy Population: The Bone Biopsy Population will consist of all subjects who have completed both their baseline and randomized 1, 2, or 4 year bone biopsies. This will include subjects from cohorts 2 and 3.

Secondary Efficacy Population: This population consists of all subjects who received at least one dose of hPTH and had at least one post-baseline non-biopsy efficacy assessment. This will include subjects from cohorts 2 and 3.

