7.4 Analysis Methods

All study endpoints used in analyses will be summarized in tables. Continuous endpoints will be summarized over time using n, mean \pm se, median, min, max. Endpoints requiring log-transformation will also be summarized over time using geometric means with their 95% confidence limits. Ordinal endpoints will be summarized using medians, min, max, and their 10th and 90th percentiles. Categorical endpoints will be summarized using number and percent in each category.

All efficacy analyses related to the bone biopsies will be performed on the Bone Biopsy Population. All efficacy analyses other than the bone biopsy related endpoints will be performed on the Secondary Efficacy Population.

For subjects who enter menopause during the study, any of their efficacy endpoints collected during or post-menopause will be excluded from the efficacy analyses, and will have such endpoints reported separately in the subject listings.

Unless otherwise stated, all statistical inference will be based on an alpha level of 0.05 with adjustments for multiple comparisons when needed as described below. Analyses will be made using SAS (SAS Institute, Cary, North Carolina), version 9.4 or later.

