7.4.1 Primary Efficacy Analyses

Separate primary analyses will be performed for each of the eight primary bone structure and bone remodeling biopsy endpoints listed in section 7.2.1. Since the study was terminated early and is thus under-powered, no corrections for multiplicity will be made in the analyses of the 8 primary efficacy endpoints. For each of these primary bone biopsy endpoints, the primary analysis will test for differences with respect to the time of the biopsy (baseline, 1, 2, and 4 year). These endpoints will be analyzed using repeated measures mixed models with the bone biopsy endpoint as the dependent variable, the baseline value of the bone biopsy endpoint and study cohort as covariates, biopsy time (baseline, 1 year, 2 year, and 4 year) as the repeated measure, and subject as the random variable. The repeated measures will include a time-dependent covariate to adjust the baseline biopsy of Cohort 2 for the time delay between the baseline biopsy and the start of hPTH treatment. This covariate will adjust Cohort 2 for any possible further progression of disease occurring between the baseline biopsy measures and the start of hPTH therapy. An indicator variable in the statistical model will set the effects of this time-dependent covariate to zero for Cohort 3 and for the post-baseline biopsies of Cohort 2.

Pairwise contrasts between the bone biopsy times will be performed within the repeated measures analyses to compare the effects of the biopsy times on the bone biopsy endpoints. Because the sample size for 2-year and 4-year biopsies are reduced in size due to withdrawal and the early termination of the study, the 2-, and 4-year biopsies may be combined into one group provided their effects are qualitatively similar (i.e. the estimates of their effects are in the same direction). If the 2- and 4-year biopsies are qualitatively different then the 4-year biopsies may be dropped from the analysis due to its small sample size. The post hoc pairwise comparisons among the

biopsy time-points will be corrected for multiple comparisons using Fisher's protected LSD with Bonferroni corrections when the overall effect of biopsy year is not statistically significant.

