7.4.3 Other Efficacy Analyses

If there is a high study withdrawal rate before the second biopsy for reasons other than the final termination of the study then patterns associated with subject withdrawal will be analyzed with respect to the primary bone biopsy endpoints. If the patterns associated with early withdrawal suggest a possible source of bias, then a sensitivity analysis on the primary efficacy analyses using multiple imputation (Proc MI in SAS) will be employed.

The tertiary outcomes include changes in blood chemistries, FGF23, renal mineral handling, and PTH sensitivity will be analyzed using repeated measures if the outcome is continuous or using contingency tables for categorical outcomes. Results will be summarized in tables. Figures will be provided upon request.

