9. CHANGES TO THE ANALYSES PLANNED IN THE PROTOCOL

The study was discontinued early, due to pharmacy issues. Upon termination of new enrollment in June of 2015, subjects began to be slowly weaned off of hPTH. Of the 32 planned, newly enrolled subjects, only 19 were actually enrolled and treated and of these, 8 subjects provided their on-treatment biopsy. This early termination provides less power to detect significant differences in endpoints. We will evaluate the possibility of combining the 2- and 4- year biopsy groups to address this issue (see section 7.4.1 for details).

The primary bone biopsy endpoints have changed. The original primary endpoints included: 1) mineralized perimeter; 2) bone formation rate; 3) cortical width; 4) cortical area; 5) osteoid width; 6) osteoid perimeter; and 7) mineral apposition rate. These primary bone biopsy endpoints have been replaced with the eight primary endpoints listed in section 7.2.1. In the analysis of the pilot study of the first 5 patients as well as other relevant pilot studies, we learned that these are the more informative indices.

The primary and secondary analyses will be performed using repeated measures mixed models rather than the paired t-tests, ANOVA, and ANCOVA analyses as stated in the protocol.

Although the protocol specifies imputation analyses for all secondary endpoints collected every 6 months over the 5-year study period, for purposes of efficiency the sensitivity analyses using multiple imputation (Proc MI in SAS) of missing values will be initially limited to the primary efficacy bone biopsy endpoints. After reviewing patterns of missing-ness in the secondary endpoints, additional sensitivity analyses involving multiple imputations may be performed at the request of the PI.

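### The Bone Biopsy Population leaves the planned multiple imputation no missing second biopsy to fill, and drops up to 11 of 19 new subjects' baseline biopsies from the mixed model

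*SAP*

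**What the plan says.** SAP section 4 defines the set: "The Bone Biopsy Population will consist of all subjects who have completed both their baseline and randomized 1, 2, or 4 year bone biopsies". It adds: "This will include subjects from cohorts 2 and 3". Section 7.4 makes it binding, with no exception for sensitivity analyses: "All efficacy analyses related to the bone biopsies will be performed on the Bone Biopsy Population".

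The primary model in 7.4.1 is a repeated-measures mixed model with "biopsy time (baseline, 1 year, 2 year, and 4 year) as the repeated measure, and subject as the random variable". The same section also enters the baseline value of the endpoint as a covariate.

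On missing data, 7.1 says the primary analysis will be repeated with imputed values if the pattern of missingness suggests bias. Section 7.4.3 gives the trigger: a high rate of withdrawal before the second biopsy, other than through the final termination of the study. If the patterns then point to bias, "a sensitivity analysis on the primary efficacy analyses using multiple imputation (Proc MI in SAS) will be employed". Section 9 still lists this imputation as planned for the primary biopsy endpoints.

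On numbers, section 9 says of the new subjects that "only 19 were actually enrolled and treated and of these, 8 subjects provided their on-treatment biopsy". On their baselines, section 4 says: "Whereas for cohort 3, baseline biopsies were taken immediately prior to beginning hPTH".

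Protocol 10.1 handled this differently. Its primary analysis used evaluable subjects only. As a sensitivity analysis it imputed each absent follow-up biopsy and compared the two results.

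**The concern.** Two parts of the SAP do not fit together. The imputation exists to examine subjects who left before their second biopsy, yet the population it is tied to admits only subjects who had that biopsy. Read literally, the check for dropout bias cannot reach the people it is about. The SAP names no wider set for it.

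The set also sits badly with the model. A pairs-only set suits the protocol's paired t-test, where a subject with one biopsy contributes nothing. The SAP replaced that test with a mixed model in which baseline is a level of the outcome, so a baseline-only subject can contribute. In a study that 7.4.1 itself calls under-powered, baseline specimens already taken are left out.

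At stake are some precision in the mean change and, more importantly, the only planned check on whether the completers represent the treated subjects.

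**Working it through.** **The plan's own figures.** Protocol 10.2 gives 93% power for a paired t-test with 8 new subjects per arm, change 10%, SD 7%, two-sided 0.05. The noncentral t with 7 df and standardized effect 10/7 gives 93.1%, so it reproduces. The protocol allowed for one third lost: 36 × 2/3 = 24 evaluable, 8 per arm.

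**Counts (SAP section 9, Cohort 3).**
- Treated: 19. With an on-treatment biopsy: 8.
- Without: 19 − 8 = 11, or 11/19 = 58%, against 33% planned.
- Missing second biopsies inside the Bone Biopsy Population: 0, by definition.
- Treated subjects with a baseline but no second biopsy: up to 11. This is an upper bound, because the SAP does not say how many baseline specimens were analysable. Cohort 2 counts are not given.

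**Precision.** Assume equal variance σ² at both times, follow-up years pooled, correlation r between baseline and follow-up, n = 8 pairs, N = 19 baselines, and baseline as an outcome level only (no baseline covariate).
- Pairs only: Var = 2σ²(1 − r)/n.
- All baselines, maximum likelihood: Var = σ²[(1 − r²)/n + (1 − r)²/N].
- Ratio = [(1 + r) + (1 − r)n/N]/2, with n/N = 8/19 = 0.421.

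| r (assumed) | Ratio, N = 19 | Reduction |
|---|---|---|
| 0 | 0.711 | 29% |
| 0.3 | 0.797 | 20% |
| 0.5 | 0.855 | 14% |
| 0.7 | 0.913 | 9% |
| 0.9 | 0.971 | 3% |

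If only 13 of the 19 baselines were usable, the ratio runs from 0.81 (r=0) to 0.98 (r=0.9). These are large-sample values. With the covariance estimated from 8 pairs the gain is smaller, possibly none at r = 0.7.

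**The model as written.** Section 7.4.1 uses baseline both as an outcome level and as a covariate, so for a baseline-only subject the outcome and the covariate are the same number. Simulation of that model (compound symmetry, one pooled follow-up) gives a variance reduction of about 16% at r = 0 and 8% at r = 0.5, roughly half of the table values.

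**Bias, if loss depended on baseline.** Assume the log-odds of having the second biopsy rise by 1 per SD of baseline, with r = 0.5 and a true change of 1.00 SD.
- Completers only: 0.77, so 0.23 SD too small.
- Full set, no baseline covariate: about 1.00.
- Full set, covariate kept: 0.83, so 0.17 SD too small. That leaves 0.17/0.23 = 74% of the bias.

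The completers' bias equals (1 − r) times their mean baseline in SDs; 0.23 at r = 0.5 corresponds to a mean of 0.46. If loss ran the other way the sign would reverse.

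**The case against.** **The evaluable set was the protocol's choice.** Protocol 10.1 made evaluable subjects primary and imputation secondary. That is true, and it is a reason to keep the both-biopsies analysis. But the protocol's imputation did cover the absent biopsies, and the SAP's population rule removes that coverage.

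**The intent is clear enough.** Sections 7.1 and 7.4.3, read with the protocol, plainly mean to bring the withdrawn subjects back, and one sentence naming the imputation population would cure it. This stands for the imputation. It does not deal with the baselines dropped from the mixed model.

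**Saying that nothing at all could be imputed goes too far.** A reader might infer this, but the documents do not support it. Section 7.4 excludes endpoints collected during or after menopause, so a completed second biopsy can still become missing, and a single index may be unmeasurable on a specimen. The accurate statement concerns absent second biopsies, which are what the protocol's imputation targeted.

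**The completers' result has not been shown to be biased.** A reader might infer bias from 58% loss, or from the withdrawal rule for low bone density. The split of the 11 between withdrawal and study termination is not reported, and loss through termination need not depend on baseline. Low density is an exclusion at entry, and the withdrawal rule in protocol section 8 is triggered by a fall on treatment. Nothing in the documents ties it to baseline histomorphometry.

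**The precision gain is small if r is high.** It is. Even in the baseline-dependent scenario without the covariate, the root mean squared error is 0.39 against 0.42 for completers, because the standard error rises as the bias falls.

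**Conclusion.** The concern holds as an inconsistency in the SAP with a modest statistical cost. On the stated population, the imputation planned for withdrawal before the second biopsy has no missing second biopsy to fill. Separately, up to 11 of 19 Cohort 3 baselines are left out of a model that could use them.

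Without the baseline covariate, the large-sample variance reduction from keeping them is about 29%, 14% and 9% at r = 0, 0.5 and 0.7. This rests on an r that is not in the documents, equal variances, pooled follow-up years and all 19 baselines being usable. The realised gain with 8 pairs would be lower.

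A reader might infer that widening the population alone removes any dropout bias. It does not under the 7.4.1 model: in the assumed scenario the estimate moves only from 0.77 to 0.83 against a true 1.00. The baseline covariate has to go as well. The scenario itself is an assumption; baseline-dependent loss is possible but not demonstrated. The stronger reason to change the plan is that its dropout check cannot work as written.

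**What to change.** 1. In SAP section 4, add a full biopsy set: Cohort 2 and 3 subjects with a baseline biopsy and at least one hPTH dose.
2. In 7.4 and 7.4.1, fit the primary mixed model to all available biopsies in that set. Keep the current both-biopsies set as the evaluable (completers) analysis and report it alongside.
3. In 7.4.1, drop the baseline value as a covariate, since baseline is already a level of the repeated outcome.
4. In 7.1 and 7.4.3, name the full biopsy set as the population for the multiple imputation.
5. Report by cohort how many subjects had each biopsy, and whether an absent second biopsy was due to withdrawal or to study termination.

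This takes a few sentences of SAP text and no new data collection. The cost is that the primary result then relies on a missing-at-random assumption, which is why the completers analysis should stay beside it. If the sponsor prefers to keep completers as primary, item 4 is the minimum.
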